**Historical Protocol Versions**

Version 1: 4/12/21

Version 2: 8/16/2022

Version 3:

**LIST OF ABBREVIATIONS**

Abbreviation or Term 	Definition/Explanation
AE	Adverse event
ALT	Alanine aminotransferase
ANCOVA	Analysis of covariance
ANOVA	Analysis of variance
APTT	Activated partial thromboplastin time
AST	Aspartate aminotransferase
AV	Atrioventricular
β-HCG	Beta-human chorionic gonadotropin
BID	Twice daily
BLQ	Below limit of quantification
BMI	Body mass index
BP	Blood pressure
BUN	Blood urea nitrogen
Ca ++	Calcium
CBC	Complete blood count
CFR	Code of Federal Regulations
CHF	Congestive heart failure
CI	Confidence interval
Cl-	Chloride
CL cr	Creatinine clearance
C max	Maximum observed concentration
C min	Trough observed concentration
CNS	Central nervous system
CR	Complete response
CRF	Case report form
CT	Computed tomography
CTCAE	Common Toxicity Criteria for Adverse Events

Abbreviation or Term 	Definition/Explanation
CV	Coefficient of variation
CYP	Cytochrome P450
D/C	Discontinue
ECOG	Eastern Cooperative Oncology Group
eCRF	Electronic case report form
DLT	Dose Limiting Toxicity
ECG	Electrocardiogram
Eg	Exempli gratia (for example)
FACS	Fluorescence Activated Cell Sorting
FDA	Food and Drug Administration
FDG-PET	Fluorodeoxyglucose (FDG)-positron emission tomography (PET)
GCP	Good Clinical Practice
GFR	Glomerular filtration rate
GGT	Gamma glutamyl transferase
GLP	Good laboratory practice
HBsAg	Hepatitis B surface antigen
HBV	Hepatitis B virus
HCO 3 	Bicarbonate
HCV	Hepatitis C virus
HIV	Human immunodeficiency virus
HR	Heart rate
hr	Hour or hours
IC 50	Half maximal inhibitory concentration
i.e.	Id est (that is)
IEC	Independent ethics committee
INR	International normalized ratio
IRB	Institutional review board
IU	International unit

Abbreviation or Term 	Definition/Explanation
IV	Intravenous, intravenously
LDH	Lactate dehydrogenase
LLQ	Lower limit of quantitation
MedRA	Medical Dictionary for Drug Regulatory Activities
MRI	Magnetic resonance imaging
MRSD	Maximum recommended starting dose
MTD	Maximum tolerated dose
NOAEL	No-observed-adverse-effect level
NOEL	No-observed-effect-level
PD	Pharmacodynamic(s)
PFS	Progression Free Survival
PK	Pharmacokinetic(s)
PO	Per os (administered by mouth)
PR	Partial response
PT	Prothrombin time
PTT	Partial thromboplastin time
QC	Quality control
RBC	Red blood cell
QD	Once daily
QTc	QT interval corrected
QTcF	QT interval corrected using Fredericia equation
SAE	Serious adverse event
SD	Standard deviation or stable disease
T 1/2	Terminal elimination half-life
T 3	Triiodothyronine
T 4	Thyroxine
T max	Time of maximum observed concentration
TID	Three times daily

Abbreviation or Term 	Definition/Explanation
TSH	Thyroid-stimulating hormone
ULN	Upper limit of normal
ULQ	Upper limit of quantitation
UV	Ultraviolet
WBC	White blood cell
WOCBP	Women of childbearing potential
WONCBP	Women of nonchildbearing potential

All of these abbreviations may or may not be used in protocol.

**Name of Institution**

## STUDY SUMMARY

Title	Systems Biology Guided Therapy for Breast Cancer Positive for Oestrogen Receptor after Aromatase Inhibitor and CDK inhibition.
Short Title	SPOCK
Protocol Identifiers (IRB – internal)	U21-02-4401
IND number	N/A
Phase	II
Design	
Open label, interventional
 
All patients will have a biopsy at the beginning of the trial. The biopsy will be sent for DNA sequencing through FoundationOne (clinical test) and RNA profiling at Fulgent (research test) for determination of activation of various oncogenic pathways and phenotypes. The results will be analyzed by [name] and [name], and a treatment recommendation will be made to the treating physician based on the algorithm below.
 
Biopsies will also be performed 2-4 weeks after the start of therapy for correlative purposes.

Study Duration	24 months recruitment, with up to 3 years of follow up per patient
Objectives	
Primary To determine if systems biology guided therapy can improve PFS
 
Secondary To determine the minimum turn-around time needed for systems biology analysis
 
To determine the response rate to systems biology guided therapy
 
To compare PFS based on concordance with recommended treatment

Number of Subjects	74 treated according to recommendations
Diagnosis and Main Eligibility Criteria	
 
• Metastatic or incurable breast cancer
 
• Progression while on aromatase inhibitor and CDK inhibitor
 

	
 
• Biopsiable lesion
 
• ECOG 0-2
 
• Age 18 or greater
 

Study Product, Dose, Route, Regimen	Drug determined by treating oncologist based on recommendation from systems biology analysis.
Duration of administration	Until intolerance or progression.
Reference therapy	Unguided therapy
Statistical Methodology	The PFS will be compared to 8 months, which is the approximate expected median PFS of fulvestrant +/- alpelisib as second line unguided therapy after AI+CDK inhibitor based on SOLAR-1. With a two-sided alpha of 0.1, beta of 0.2, 18 months of accrual, and 6 months of follow-up, 74 patients are needed to detect a 4 month improvement in PFS with genomic - guided therapy.

## 1 OBJECTIVES

### 1.1 Primary Objectives and Endpoint

#### 1.1.1 Primary Objective

To determine if systems biology guided therapy can improve PFS

#### 1.1.2 Primary Endpoint

Progression free survival in patients treated in concordance with recommendation

### 1.2 Secondary Objectives

To determine the minimum turn-around time needed for systems biology analysis

To determine the response rate to systems biology guided therapy

To compare PFS based on concordance with recommended treatment

## 2 BACKGROUND

Over 70% of breast cancers are positive for estrogen receptors (ER+) and do not overexpress HER2 (HER2-). These tumors are driven by estrogen and addicted to estrogen signaling, so the primary treatment for metastatic ER+, HER2- treatment is estrogen blockade. Because of the results of the PALOMA-1, MONALEESA-2, and MONARCH-3 trials, the standard of care for first-line treatment of metastatic ER+, HER2- breast cancer is aromatase inhibitor plus a CDK4/6 inhibitor(1)

The second line treatment for ER+, HER2- breast cancer is less well defined. Multiple mechanisms of resistance to aromatase inhibitors or CDK4/6 inhibitors have been described. These include ligand-independent activation of ER through increased tyrosine kinase signaling, mutations in the alpha isoform of ER, deregulated ER co-regulators, epigenetic changes, and activation of PI3K/AKT/MTOR signaling.(2) The only available tests are for mutations in these various genes, and of these only mutations in PIK3CA have been shown to be clinically useful.(3)

The NCCN lists multiple options for second-line therapy of ER+, HER2- metastatic breast cancer after progression on aromatase inhibitor plus CDK4/6 inhibitors.(1) These include fulvestrant, a selective estrogen degrader, fulvestrant plus alpelisib, a PI3K inhibitor approved only when PIK3CA is mutated, exemestane plus everolimus, an MTOR inhibitor, tamoxifen, or chemotherapy. There is no biologic way to choose among these options in the absence of a PIK3CA mutation.

Gene expression profiling has become commonly used in early-stage breast cancer but is not commonly used in metastatic breast cancer. Therefore, we have developed gene expression-based biomarkers of estrogen activation in advanced breast cancer and of MTOR activation in breast cancer. We hypothesize that treatment based on these biomarkers can improve progression free survival by matching treatments to tumors with active pathways targeted by those treatments. The algorithm for treatment recommendations is shown in figure 1.

[figure not shown]

Figure 1: Algorithm for Treatment Recommendations

## ENDORSE

ENDORSE is a 63-gene gene expression signature to measure estrogen signaling in metastatic breast cancer. It was derived from 833 ER+, HER2- tumors from

METABRIC, a database of gene expression data for breast cancer. ENDORSE was validated in data from an independent cohort assessing 140 patients with metastatic ER+ breast cancer treated with endocrine therapy, over three quarters of which had received prior endocrine therapies. ENDORSE was able to separate those with short survival with endocrine therapy from those

[figure not shown]

Figure 2: Survival after endocrine therapy for women with metastatic ER-positive, Her2-negative breast cancer based on classification by the ENDORSE signature of estrogen pathway activation. Low Risk = High estrogen activation, High Risk = low estrogen activation.

with long survival (figure 2). ENDORSE was also validated by showing it could predict the decrease in Ki-67 in two neoadjuvant trials of fulvestrant. ENDORSE is not predictive in HER2+ or ER- breast cancers, showing it is a true marker of estrogen signaling activation.

## MTOR Signature

No datasets exist with gene expression data from patients with ER+ breast cancer treated with MTOR inhibitors. (BOLERO-2 collected gene expression data but due to consent issues that data has now been destroyed). Therefore, we derived the MTOR signature

[figure not shown]

Figure 3: Boxplots comparing predicted probability of mTOR inhibitor response in ER+ breast cancers grouped by observed clinical response to everolimus plus aromatase inhibitor.

from gene expression data combining data from a clinical trial of everolimus in the neoadjuvant treatment of breast cancer with in vitro drug sensitivity data from a panel of 9 cell lines. We used machine learning to develop a 97-gene gene expression signature for predicting the ability of everolimus to decrease proliferation in breast tumors. Results of internal validation are shown in the figure. Since no other dataset exists with gene expression data in metastatic breast cancer prior to treatment with everolimus, no MTOR signature can be externally validated. Because exemestane/everolimus and fulvestrant are both FDA approved in the population eligible for SPOCK and this is not a curable population, we consider it appropriate to proceed

without external validation, noting that this trial will provide a dataset that can be used for validation of predictors by us and others in the future.

### **3 DRUG INFORMATION**

N/A

### **4 STUDY DESIGN**

#### **4.1 Description**

Single-arm, open label phase II trial.

#### **4.2 Number of Patients**

66 evaluable patients, 74 total to account for dropout

#### **4.3 Number of Study Centers**

2-5

#### **4.4 Study Duration**

24 months of recruitment. Maximum 3 years of follow up.

## 5 ELIGIBILITY CRITERIA

This eligibility checklist is used to determine patient eligibility and filed with signature in the patient research chart.

Patient No. \_\_\_\_\_  
Patient's Initials: (L,F,M) \_\_\_\_\_

### 5.1 Inclusion Criteria

Yes/No (Response of "no" = patient ineligible)

- \_\_\_\_ Histologic diagnosis of breast cancer (ER+, HER2-)
- \_\_\_\_ Metastatic or incurable
- \_\_\_\_ Prior treatment with an antiestrogen and a CDK4/6 inhibitor
- \_\_\_\_ Progression while on or within 6 months of stopping the CDK4/6 inhibitor
- \_\_\_\_ At least one lesion amenable to percutaneous biopsy (bone lesions are allowed as long as they are clearly progressive from tumor)
- \_\_\_\_ ECOG 0-2
- \_\_\_\_ Age 18 or greater
- \_\_\_\_ Able to provide informed consent and willing to sign an approved consent form that conforms to federal and institutional guidelines.

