### 5.2 Exclusion Criteria

Yes/No (Response of "yes" = patient ineligible)

- \_\_\_\_ Prior treatment within 2 years with alpelisib, everolimus,
- \_\_\_\_ Comorbid disease other than breast cancer with a life expectancy of less than 2 years
- \_\_\_\_ Cancer other than breast cancer that is expected to need treatment within 2 years
- \_\_\_\_ Platelets < 100,000/microliter
- \_\_\_\_ INR > 1.5

I certify that this patient meets all inclusion and no exclusion criteria for enrollment onto this study.

Investigator Signature \_\_\_\_\_ Date \_\_\_\_\_

Coordinator Signature \_\_\_\_\_ Date \_\_\_\_\_ Coordinator Signature \_\_\_\_\_ Date \_\_\_\_\_

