## **10 STATISTICAL CONSIDERATIONS**

### **10.1 Sample size determination**

This is an open-label phase II study of systems biology guided therapy for breast cancer patients positive for Oestrogen receptor after Aromatase inhibitor and CDK inhibition. Based on the SOLAR-1 trial, 25% of tumors would have PIK3CA mutation, so 25% of people would be treated with fulvestrant plus alpelisib with a median PFS in that group of 11 months and 75% of people would be treated with fulvestrant with a median PFS in that group of 6 months.(3) The weighted average of these medians is 7.25 months, but since the actual distributions of the progression free survivals are not available, we will use a conservative estimate of the expected median PFS of the historical control group (fulvestrant +/- alpelisib as second line unguided therapy) of 8 months.

Based on the preclinical assessments and assay features, it is expected that 10% of patients enrolled in the trial will be assigned to capecitabine, 25% to fulvestrant/alpelisib, 32.5% to fulvestrant, and 32.5% to exemestane everolimus. The goal is to assign people to therapy so that the capecitabine group will have a median PFS of 18 months (75th percentile of survival in BOLERO-6(5)), the fulvestrant group will have a median PFS of 10 months (75th percentile of survival in SOLAR-1(3)), and the exemestane/everolimus group will have a median PFS of 13 months (25th percentile of BOLERO-2(6)). From the results of the BOLERO-2 trial, BOLERO-6 trial, and the SOLAR-1 trial, it is hypothesized that the weighted median PFS with genomic- guided therapy will be improved to 12.1 months from 9 months of fulvestrant +/- alpelisib as second line unguided therapy after AI+CDK inhibitor.

With an alpha of 0.1, beta of 0.2, 18 months of accrual, and 6 months of follow-up, 66 patients are needed to detect a 4-month improvement in the median PFS (from 8 months to 12 months) with genomic- guided therapy, assuming an exponential distribution using a 2-sided Log-rank test. Accounting for 10% loss, the trial will enroll 74 eligible patients.

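### The 8-month benchmark is defined for second-line therapy after an aromatase inhibitor plus CDK inhibitor, but eligibility and the primary analysis are not confined to such patients, and the Summary and Section 5.1 differ on who they are

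*Combined protocol and SAP*

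**What the plan says.** **Eligibility.** The Study Summary lists among its main criteria "Progression while on aromatase inhibitor and CDK inhibitor". The Section 5.1 checklist has two items instead: "Prior treatment with an antiestrogen and a CDK4/6 inhibitor" and "Progression while on or within 6 months of stopping the CDK4/6 inhibitor". Section 5.2 has one exclusion that bears on earlier lines: "Prior treatment within 2 years with alpelisib, everolimus". Neither the Summary nor Section 5 states a maximum number of prior lines.

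**Benchmark.** The Summary compares PFS with 8 months, "which is the approximate expected median PFS of fulvestrant +/- alpelisib as second line unguided therapy after AI+CDK inhibitor based on SOLAR-1". Section 10.1 describes the historical control in the same terms, "fulvestrant +/- alpelisib as second line unguided therapy after AI+CDK inhibitor". It builds the figure from two components. The first is that "25% of people would be treated with fulvestrant plus alpelisib with a median PFS in that group of 11 months". For the second, the remaining three quarters are assumed to receive fulvestrant alone, at a 6-month median.

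**Analysis set.** Section 10.2.1 makes all enrolled patients with concordant therapy evaluable for the primary endpoint. It has no restriction, stratification or sensitivity analysis by line of therapy or prior endocrine partner.

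**The concern.** Section 4.1 describes a single-arm trial, so there is no concurrent control to absorb differences in case mix. Whether guided therapy has improved PFS is judged against one fixed number. That number is a valid reference only if 8 months is about what the enrolled patients would have achieved without guidance.

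The benchmark specifies an AI partner and second-line treatment. Section 5.1 specifies neither. A patient whose CDK4/6 inhibitor was paired with another antiestrogen, or who has had further treatment since, can satisfy the checklist and enter the primary analysis. If such patients are numerous and their prognosis differs, the result mixes the effect of guidance with the effect of case mix. A useful algorithm could then appear to fail, or a useless one could appear to work.

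**Working it through.** **1. Passages side by side**

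| Feature | Summary eligibility | Section 5.1 / 5.2 | Benchmark (Summary, 10.1) |
|---|---|---|---|
| Endocrine partner | AI | any antiestrogen | AI |
| Timing of progression | on treatment | on the CDK4/6 inhibitor, or up to 6 months after stopping | not stated beyond following AI+CDK inhibitor |
| Line of therapy | not stated | not stated; alpelisib or everolimus within 2 years excluded | second line |

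The two eligibility statements conflict on partner and timing. On line of therapy both are silent, and only the benchmark specifies it. Section 10.2.1 uses the word antiestrogen generically when it defines concordance for the fulvestrant group, so the term in 5.1 cannot safely be read as AI only.

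**2. The plan's own figures**

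Benchmark: 0.25 × 11 + 0.75 × 6 = 7.25 months, which Section 10.1 raises to 8. Neither component is broken down by line or prior partner.

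Sample size inputs (Summary and 10.1): medians 8 and 12 months, exponential PFS, two-sided alpha 0.10, power 0.80, 18 months of accrual, 6 months of follow-up.

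- Events = (1.645 + 0.842)² / [ln(8/12)]² = 6.185 / 0.1644 = 37.6.
- With λ = ln 2 / 12 = 0.0578, P(event) = 1 − (e^(−6λ) − e^(−24λ)) / (18λ) = 1 − (0.707 − 0.250) / 1.040 = 0.560.
- N = 37.6 / 0.560 = 67.1. A version on the hazard-difference scale, with separate null and alternative variances, gives 66.4.
- Loss: 66 / 0.9 = 73.3, rounded up to 74.

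The plan's 66 and 74 are therefore reproduced for an 8 versus 12 month comparison.

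**3. Illustration: some patients fall outside the benchmark description**

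The setting is n = 66, uniform accrual over 18 months plus 6 months of follow-up, and exponential PFS. The test is a one-sample log-rank test against 8 months, z = (E − O)/√E, where O is the observed number of events and E the number expected at an 8-month median. Improvement is declared if z > 1.645. Section 10.2.1 does not describe the test, so this form is my assumption. Benchmark-type patients have a guided median of 12 months. The share of other patients and their guided median are also assumptions, because the documents give neither.

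| Share outside benchmark | Guided median 9 months | Guided median 7 months |
|---|---|---|
| 0% | 82% | 82% |
| 10% | 76% | 71% |
| 20% | 71% | 59% |
| 30% | 64% | 45% |

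Entries are power. Repeat runs of 20,000 to 40,000 trials agreed to within about one percentage point.

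**4. The other direction**

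Here the benchmark stays at 8 months and the true unguided median of the whole enrolled mix varies (again an assumption).

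| True unguided median | False-positive rate, no effect | Power if hazard ratio is 2/3 |
|---|---|---|
| 7 months | 0.4% | 53% |
| 8 months | 4% | 81% |
| 9 months | 17% | 95% |
| 10 months | 40% | 99% |

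The error can run either way.

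**5. Size of a benchmark-matching subset**

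If 20% or 30% fall outside, the subset is 66 × 0.8 ≈ 53 or 66 × 0.7 ≈ 46 patients. By the same simulation at a 12-month median, power is about 74% or 68%.

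**The case against.** The Summary row is headed as the main criteria and is an abbreviation. Sections 5 and 11 make the checklist operative, so site staff have one rule to follow. The 6-month item can be read as the current, study-qualifying progression, which would place most entrants in the line directly after CDK4/6 inhibition. The 2-year exclusion removes patients who recently received two of the second-line drugs listed in Section 2. Broad eligibility is also a legitimate choice in a phase II trial.

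Much of this stands. It limits how far the mismatch is likely to reach, and it rules out saying that the protocol expressly admits any number of lines; that is only an inference from the absence of a cap. It does not close the gap. The text does not tie the qualifying progression to the most recent line. The AI-versus-antiestrogen difference remains however the 6-month item is read. The sample size rests on the narrower description.

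A reader might infer that the Summary and 5.1 contradict each other on line of therapy. They do not; neither mentions it. A reader might also assume that the extra patients must shorten PFS, so that any bias is conservative. The documents contain no PFS figure for later-line or non-AI patients, so that direction cannot be established from them.

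**Conclusion.** The point holds as a question of whether the benchmark fits the patients enrolled, together with two textual conflicts on eligibility: AI versus any antiestrogen, and progression on treatment versus up to 6 months after stopping. The eligible set includes the benchmark population, so the 8-month figure may fail to describe part of the enrolled patients, not all of them. The size of that part is unknown.

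It would be too strong to call the stated 80% power untrue or the sample size wrong. N = 66 is reproduced, and its power is conditional on case mix. The power losses in the working, from about 6 points (10% of patients, 9-month median) to about 37 points (30%, 7-month median), depend entirely on assumed shares and medians. They model a subgroup with a shorter guided PFS, and none of them measures the effect of the AI/antiestrogen wording or the 6-month window as such. The change is worth making because it is cheap and the trial has no other comparator.

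**What to change.** 1. Reconcile the Summary, Section 5.1 and Section 10.1 on prior endocrine partner, the 6-month window and the line of therapy the benchmark assumes. Which criterion is right is for the investigators; this review does not choose one.
2. Add CRF fields for number of prior lines and prior endocrine partner. Section 8 takes a medical history at screening, but Section 12 restricts data capture to endpoints and information needed for planned manuscripts, so these items must be named explicitly.
3. In Section 10.2.1, prespecify the comparison with 8 months in patients who are in the next line after AI plus CDK inhibitor, as a named sensitivity analysis of the primary endpoint.

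The cost is wording, two CRF fields and one analysis. Accrual is unaffected if the reconciled text does not narrow eligibility. The drawback is precision: with about 53 or 46 patients, power is about 74% or 68%, so the analysis helps to interpret the primary result and cannot replace it.

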### 5.2 Exclusion Criteria

Yes/No (Response of "yes" = patient ineligible)

- \_\_\_\_ Prior treatment within 2 years with alpelisib, everolimus,
- \_\_\_\_ Comorbid disease other than breast cancer with a life expectancy of less than 2 years
- \_\_\_\_ Cancer other than breast cancer that is expected to need treatment within 2 years
- \_\_\_\_ Platelets < 100,000/microliter
- \_\_\_\_ INR > 1.5

I certify that this patient meets all inclusion and no exclusion criteria for enrollment onto this study.

Investigator Signature \_\_\_\_\_ Date \_\_\_\_\_

Coordinator Signature \_\_\_\_\_ Date \_\_\_\_\_ Coordinator Signature \_\_\_\_\_ Date \_\_\_\_\_

## 6 TREATMENT PLAN

### 6.1 Patient enrollment

Once a patient signs the informed consent form, she/he may be screened. If all inclusion/exclusion criteria are met, then they are enrolled. During screening a biopsy site will be identified. In accordance with the ASCO Ethical Framework for Mandatory Research Biopsies, because the biopsy results are used in the primary endpoint of the study, the biopsy risk may be low or moderate risk (expected rate of major complications < 1.5%), including biopsy of bone marrow, skin, superficial masses, intra-abdominal masses, peripheral thoracic masses that can be accessed without penetrating lung, or sites that will be biopsied for other clinical purposes.

Note that after patients may be continued on the most recent therapy up to the biopsy at the discretion of the treating oncologist. After the biopsy, the treating oncologist may opt to start a new therapy while waiting for results and then switch based on results if desired. No wash-out period necessary.

